A prospective randomized trial comparing Restorelle® Y mesh vs. Vertessa® lite Y mesh for laparoscopic and robotic-assisted laparoscopic sacrocolpopexy

[name] MPH; Assistant Professor of Surgery. Center for Urogynecology and Pelvic Reconstructive Surgery; Obstetrics/Gynecology and Women's Health Institute, Cleveland Clinic, Cleveland OH

[name] [name]; Professor, Section Head of the Center for Urogynecology and Pelvic Reconstructive Surgery; Obstetrics/Gynecology and Women's Health Institute, Cleveland Clinic, Cleveland OH

Background and Significance:

Abdominal sacrocolpopexy is considered the gold standard for vault prolapse, and has demonstrated superior anatomic outcomes compared to transvaginal suspension procedures. Laparoscopic sacrocolpopexy has become an alternative to open abdominal sacrocolpopexy as this mode of surgery bridges the gap between the advantages of vaginal surgery, namely decreased morbidity and faster patient recovery, with the surgical success rates of abdominal sacrocolpopexy (1). For young women who are sexually active with symptomatic pelvic organ prolapse, reconstruction with a sacrocolpopexy procedure is beneficial because the success rates are high as the procedure adequately restores support of the vaginal apex and maintains vaginal length (2). Robotic-assisted laparoscopic sacrocolpopexy has also emerged as a mode of vaginal vault prolapse surgery, and is a good option for patients with significant body mass index, or known pelvic adhesive disease that may make a conventional laparoscopic approach more challenging.

Sacrocolpopexy involves suspension of the vagina to the anterior longitudinal ligament of the sacrum at the level of S1 using a bridging graft which can be made of biologic or synthetic materials. The graft is sutured to the anterior as well as the posterior vagina and then attached to the anterior longitudinal ligament of the sacrum. There are a number of prosthetic materials available for use in pelvic reconstructive surgery, including sacrocolpopexy. Mersilene was a popular prosthetic for many decades, but its use rapidly declined in favor of polypropylene which is now the most commonly used synthetic product (3). The ideal prosthetic material is biocompatible, inert, has minimal allergic or inflammatory reaction, is sterile, non-carcinogenic, resistant to infection, and avoids shrinkage and mechanical stress and is easy to handle and readily available at a reasonable cost (4). Additionally, pore size of the graft material affects resistance to infection and cellular infiltration and also the flexibility of the mesh (5). Lastly, the interaction at the tissue interface of the graft material is also very important, with the ideal prosthesis causing minimal initial inflammatory and cellular response followed by adequate vascular and fibroblastic infiltration (6). Many different materials have been used as a graft in sacrocolpopexy including biologic materials (fascia lata, rectus fascia, dura mater) and synthetic materials (polypropylene mesh, polyester fiber mesh, polytetrafluoroethylene mesh, Dacron mesh, and Silastic silicone rubber). Large pore light-weight polypropylene mesh is a monofilament graft and is most commonly used

today as it meets the above-mentioned requirements, and likely has fewer complications compared to other synthetics because of these characteristics (2). Both the Restorelle® Smartmesh (Coloplast, Inc., Minneapolis, MN, USA) and the Vertessa® lite mesh (Caldera Medical. Inc., Agoura Hills, CA, USA) are ultra-light macroporous polypropylene mesh grafts that are intended for pelvic floor reconstruction. Currently, both types of grafts are used to perform sacrocolpopexy.

In our urogynecology practice at Cleveland Clinic, we currently routinely use the Restorelle® Smartmesh and we have experienced good clinical outcomes using this graft. This mesh seems to have been widely adopted by many surgeons performing sacrocolpopexy. To our knowledge, the only prospective study that exists looking at this mesh at the time of sacrocolpopexy was published by Salamon et al. (7) in 2013 in the International Urogynecology Journal. In this study, the authors sought to prospectively evaluate the use of Restorelle® Y mesh for robotic sacrocolpopexy. They implanted a total of 120 patients and obtained one year follow-up data from 118 of these patients. They reported an anatomic success rate of 89%, a subjective cure rate of 94% and no mesh erosions. Currently no prospective data exists on the Vertessa® lite mesh for sacrocolpopexy. It is used by many surgeons, but there are no data showing that it is as efficacious in treating prolapse and avoiding mesh erosion in those patients undergoing sacrocolpopexy. Therefore, the primary objective of the proposed study is to compare outcomes between the Restorelle® Y mesh and Vertessa® lite Y mesh at the time of laparoscopic and robotic-assisted laparoscopic sacrocolpopexy.

Hypothesis: Vertessa® lite Y mesh is not inferior to Restorelle® Y mesh for the treatment of vaginal vault prolapse.

Study Design: Randomized single-blind non-inferiority trial

Primary Outcome:

Composite outcome measure of surgical success:

- (1) descent of the vaginal apex more than one-third into the vaginal canal
- (2) anterior or posterior vaginal wall descent beyond the hymen
- (3) bothersome vaginal bulge symptoms
- (4) retreatment for prolapse by either surgery or pessary

Secondary Outcomes:

1. Intraoperative, peri-operative and post-operative complications
2. Pelvic floor symptoms (urinary, bowel, prolapse, sexual function): PFDI, ISI, PISQ)
3. Retreatment for urinary incontinence

Study Population: Study subjects will be recruited from patients that present to the Center for Urogynecology & Pelvic Reconstructive Surgery in the Department of Obstetrics and Gynecology at the Cleveland Clinic Main campus, Hillcrest Hospital and Fairview Hospital, and their surgeries will be performed at either one of these sites.

Inclusion Criteria:

- Age ≥ 18 , who are to undergo laparoscopic or robotic laparoscopic sacrocolpopexy for pelvic organ prolapse
- Other concomitant laparoscopic or prolapse and anti-incontinence procedures (e.g., laparoscopic supracervical hysterectomy, cystocele repair, rectocele repair or mid-urethral sling procedures) will be performed at the primary surgeon's discretion.

Exclusion Criteria:

- Inability to comprehend written and/or spoken English
- Inability to provide informed consent
- Medical illness precluding laparoscopy
- Need for concomitant surgeries not related to pelvic organ prolapse or incontinence
- Sacrocolpopoperineopexy
- Need for dual flat mesh for sacrocolpopexy procedure (determined by surgeon)

Study Procedures:

Study Identification and Recruitment

Potential subjects will be identified by members of the Center for Urogynecology & Pelvic Reconstructive Surgery at the Cleveland Clinic Main campus and Fairview Hospital. Eligible patients that agree to participate will be provided written informed consent administered by the collaborators listed on this IRB.

Randomization

All subjects will be predetermined by their surgeon to undergo either a laparoscopic or robotic assisted laparoscopic sacrocolpopexy depending upon their clinical evaluation. The participants will then be randomized to either Restorelle® or Vertessa® Y sacrocolpopexy according to a computer-generated randomization schedule with random block sizes with the use of the SAS statistical software package (SAS Institute, Cary, NC). All patients will be blinded to their assignment.

Office Interventions

All patients will be seen for a preoperative visit and then postoperatively at 6, 12 and 24 months. At each visit, a vaginal exam and a complete Pelvic Organ Prolapse Quantification (POP-Q) exam will be performed. Patients will also be asked to update their medical history. In addition, patients will be asked to complete the Pelvic Floor

Distress Inventory (PFDI-20), Incontinence Severity Index (ISI) and Pelvic Organ Prolapse/Urinary Incontinence Sexual Questionnaire (PISQ-12) questionnaires at the pre-operative visit as well as the 6, 12, and 24 month postoperative visits. Completion of these questionnaire is the only additional assessment that is specific to participation in this study and is not usually included as part of the standard care of sacrocolpopexy. It should take no more than 10-15 minutes to complete the questionnaires. The study subjects will not be exposed to any additional risk by participating in this study except for the inconvenience of completing the questionnaire.

Surgical Interventions

Laparoscopic sacrocolpopexy will be performed using four ports: an umbilical port for the laparoscope, two ports (either 5 or 10/12 mm) in the bilateral lower quadrants, and one 5-mm port placed at the level of the umbilicus, lateral to the rectus muscle on either side for retraction. The robotic-assisted hysterectomy will be performed using the da Vinci Surgical System (Intuitive Surgical Inc., Sunnyvale, CA, USA) using five ports: a 12mm umbilical port for the laparoscopic, two 8 mm robotic ports placed 2cm inferior and 9-10cm lateral to the umbilicus bilaterally, an 8mm robotic port placed in the left axillary line at the level of the umbilicus, and a 8mm or 10/12mm accessory port either in the right upper quadrant approximately 3cm distal from the costal margin, or in the right lower quadrant, 2cm above and medial to the anterior superior iliac spine.

If a supracervical hysterectomy is to be performed, it will be done in a standard fashion. A uterine manipulator will be placed inside of the uterus. The round ligaments will be transected using cautery. The fallopian tubes and ovaries will be left in situ or removed at the time of hysterectomy depending upon the preoperative decision made between the surgeon and patient. The uterine arteries and cardinal ligaments will be cauterized laparoscopically. The uterus will be amputated at the level of the internal cervical os and the endocervical canal will be cauterized.

The sacrocolpopexy will also be performed and in a standard fashion. An end-to-end anastomosis (EEA) sizer will be placed in the vagina for manipulation of the apex as well as in the rectum for delineation of the rectovaginal septum. First, the presacral dissection will be performed with a longitudinal peritoneal incision over the sacral promontory and there is identification of the anterior longitudinal ligament. Dissection is then done caudally through the peritoneum and subperitoneal fat down to the level of the posterior cul-de-sac. The vagina is elevated cephalad using the EEA sizer and the peritoneum overlying the anterior vaginal apex is incised transversely, and the bladder is dissected off the anterior vagina using sharp dissection, creating a 4 to 5 cm pocket. If this plane is difficult to establish, the bladder will be filled in a retrograde fashion to find the correct dissection plane. Similarly, the peritoneum overlying the posterior vagina is incised, and dissection is then done overlying the vagina and extending into the posterior cul-de-sac, creating a 4 to 5 cm pocket. Once dissection is complete, the mesh graft is prepared. Subjects will have been randomized to either one of two mesh grafts:

The Y mesh is introduced into the pelvis through one of the ports. First, either the anterior or the posterior arm is fixed to the anterior or posterior vaginal wall using 6

delayed-absorbable (PDS) No. 2-0 sutures in an interrupted fashion, 1 to 2 cm apart from each other. The opposing arm of the graft is then attached to either the anterior or posterior vaginal wall, depending on which arm was placed first, in a similar fashion using 6 delayed-absorbable (PDS) No. 2-0 sutures in an interrupted fashion, 1 to 2 cm apart from each other. The stem portion of the graft is then brought to the sacral promontory and sutured to the anterior longitudinal ligament using 2 permanent (prolene) No. 0 sutures. The excess mesh is then trimmed.

The peritoneum is then closed over the exposed graft with absorbable suture. Routine cystoscopy will also be performed in order to assess for lower urinary tract injury. A vaginal exam is performed, and an anterior and/or posterior colporrhaphy and perineorrhaphy are performed if needed. Anti-incontinence procedures may also be performed if needed.

**In laparoscopic cases, all suturing will be done extracorporeally while intracorporeal knot-tying technique will be performed in robot assisted laparoscopic cases.

Data Collection & Management:

Preoperative data will include the following:

- Patient age, race, vaginal parity, menopausal state, BMI, prior prolapse surgery, preoperative prolapse stage
- PFDI-20, ISI, PISQ-12
- Preoperative hemoglobin

Data points recorded during the procedure will include:

- Total OR time = operating room time of entry and exit
- Total Case time = time from incision to closure
- Concomitant procedures
 - Supracervical hysterectomy
 - Anterior colporrhaphy
 - Posterior colporrhaphy
 - Perineorrhaphy
 - Midurethral sling
- Estimated blood loss
- Intraoperative complications
 - EBL > 500cc
 - Vascular Injury
 - Cystotomy
 - Ureteral Injury
 - Bowel Injury - small bowel, large bowel, rectal

Postoperative data will include the following: 6, 12, 24 months

- POP-Q exam (performed by a provider blinded to the mesh used at the time of the procedure)
- PFDI-20, ISI, PISQ-12

- Review of electronic medical record (inpatient notes, d/c summary, ER visits), assessing for postoperative complications
 - Reoperation for immediate complications = reoperation within 30 days of surgery
 - Abdominal Wound infection = fascial, subcutaneous, cutaneous infection requiring antibiotic treatment
 - Hematoma = intrapelvic/abdominal
 - Vaginal cuff cellulitis/Pelvic Abscess = requiring IV/PO antibiotic therapy and/or transvaginal, transgluteal or percutaneous drainage
 - DVT/PE = diagnosed with Doppler US or CT scan
 - Reoperation for SUI with pubovaginal sling (synthetic or fascial), colposuspension, injection with periurethral bulking agents
 - Reoperation for mesh exposure
 - Reoperation for recurrent POP
 - Bowel Injury/Bowel Obstruction = enterotomy, perforation, ileus, partial/complete obstruction
 - Port site or incisional hernia
 - Need for any radiologic imaging
 - Lower urinary tract injury = bladder, ureteral
 - Neurologic Injury = brachial plexus, abdominal wall (ilioinguinal, iliohypogastric), lower extremity (femoral, sciatic, common peroneal)
 - Pulmonary complications = pneumonia, pulmonary hypertension, pulmonary edema within 14 days of surgery
 - Cardiac = ACS, MI, HF within 14 days of surgery
 - Postoperative ICU admission

[figure not shown]
Protection of each subject's personal health information will be a priority in this study. One master excel file containing subject personal information including name and medical record number will be kept in a password-protected file, on a designated protected research drive on a password-protected computer in a locked office at the Cleveland Clinic. In that file, each subject will be assigned a subject identification number that will be used for the purposes of data collection in order to de-identify subjects.

All paper forms used for data collection will be kept in a research cabinet dedicated to this project which will be locked at all times, in a locked office at the Cleveland Clinic. All forms will contain de-identified information – identification numbers will correspond to the subjects listed in the master excel file.

All study data will be transferred and managed electronically using REDCap (Research Electronic Data Capture). Each subject will be entered into REDCap using the assigned identification number from the master excel file. REDCap is a secure, web-based application designed to support data capture for research studies, providing user-friendly web-based case report forms, real-time data entry validation, audit trials, and a de-identified data export mechanism to common statistical packages. The system was developed by a multi-institutional consortium which was initiated at Vanderbilt University and includes the Cleveland Clinic. The database is hosted at the Cleveland Clinic Research Datacenter in the JCN basement and is managed by the Quantitative Health Sciences Department. The system is protected by a login and Secure Sockets Layers (SSL) encryption. Data collection is customized for each study as based on a study-specific data dictionary defined by the research team with guidance from the REDCap administrator in Quantitative Health Sciences at the Cleveland Clinic.

Analysis Plan:

There will be 2 arms to this study: laparoscopic (robotic-assisted and conventional) sacrocolpopexy with Restorelle® Y mesh and laparoscopic (robotic-assisted and conventional) sacrocolpopexy with Vertessa® Y mesh. Subjects will be chosen based on surgeon preference to either undergo RA LSC ASC or conventional LSC ASC. They will then be randomized to either the Restorelle® or Vertessa® Y mesh arm. We determined that if there is no difference between the two Y mesh grafts, 90 patients are required to be 70% sure that the upper limit of a one-sided 95% confidence interval will exclude a difference in favor of the Restorelle® group of more than 10%. We will account for a potential 10% subject drop out and loss to follow-up as well as unforeseen factors in recruiting and will plan to recruit 50 subjects to each arm, for a total of 100 subjects.

All statistical analyses will be done using jmp 12. We will use descriptive statistics to show our demographic and baseline data: categorical variables will be presented as n/N (%) with 95% confidence intervals and continuous variables will be presented as mean +/-SD [range]. The two Y mesh grafts will be compared. Differences between the groups in the primary outcome of surgical success and other categorical outcomes were evaluated using generalized linear models. We will control for LSC ASC and RA LSC ASC by performing a logistic regression.

Summary of tasks for study:

	Preop	6 mo	12 mo	24 mo
Informed consent	X			
Demographic data	X			
Randomization	X			
PFDI-20	X	X	X	X
ISI	X	X	X	X
PISQ-12	X	X	X	X
POP-Q	X	X	X	X
Review of d/c summary, chart, postop Hct, complications (ER visits, etc)		X		
Update medical history		X	X	X

References:

3. Porges RF & Smilen SW. Long term analysis of the surgical management of pelvic floor support defect. *Am J Obstet Gynecol* 1994;171:1518–1528.
4. Birch C. The use of prosthetics in pelvic reconstructive surgery. *Best Pract Res Clin Obstet Gyn* 2005;19(6):979-991.
5. Chu CC & Welch L. Characterisation of morphological and mechanical properties of surgical mesh fabrics. *J Biomed Res* 1985;19:903–916.
6. Kaupp HA, Matulewicz TJ & Lattimer GL. Graft infection or graft reaction? *Arch Surg* 1979;114:1419-1423.

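### Does the missing time point for the composite primary outcome leave the non-inferiority test undefined?

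*Combined protocol and SAP*

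**What the plan says.** Under Primary Outcome, the protocol lists a "Composite outcome measure of surgical success" made up of apical descent, anterior or posterior wall descent past the hymen, bothersome bulge symptoms, and retreatment for prolapse. No month is attached to the list, to the hypothesis or to the primary objective.

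Office Interventions sets the schedule: "All patients will be seen for a preoperative visit and then postoperatively at 6, 12 and 24 months". It adds: "At each visit, a vaginal exam and a complete Pelvic Organ Prolapse Quantification (POP-Q) exam will be performed". Data Collection & Management gives the three visits equal standing: "Postoperative data will include the following: 6, 12, 24 months". The task table marks the questionnaires, the POP-Q and the medical history update at all three.

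The Analysis Plan states one sample-size criterion: "90 patients are required to be 70% sure that the upper limit of a one-sided 95% confidence interval" excludes a difference of more than 10% favouring Restorelle. It then describes one comparison: "Differences between the groups in the primary outcome of surgical success" are to be assessed with generalized linear models. Neither sentence names a visit.

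The only one-year wording, in Background and Significance, describes a cited cohort: "They implanted a total of 120 patients and obtained one year follow-up data from 118 of these patients".

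**The concern.** The composite mixes conditions that can come and go (descent, bulge symptoms) with an event that accumulates (retreatment). Its value therefore depends on when it is read and on whether an earlier failure still counts once it is no longer present. Twelve months matches the cited cohort, while a cumulative reading through 24 months uses all the follow-up. Both are natural, and the same trial could pass on one and fail on the other. If the choice were made after seeing results by arm, the chance of wrongly declaring Vertessa non-inferior would exceed the nominal 5%. In a non-inferiority trial with one margin and one confidence limit, that would bear on the main conclusion.

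**Working it through.** **Inputs from the documents.** 90 evaluable patients, so 45 per arm; one-sided 95% limit; 10% margin, read as an absolute difference; 70% power with no true difference. The cited cohort's 89% anatomic and 94% subjective rates are the only success rates given, and neither is a composite rate. All other rates, and how failures accrue, are assumptions.

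**The plan's own figure.** With success rate p in both arms, power = Φ(0.10/√(2p(1−p)/45) − 1.645).

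- p = 0.95: √(2 × 0.0475/45) = 0.0459; 0.10/0.0459 − 1.645 = 0.53; power 70.2%.
- p = 0.89: √(2 × 0.0979/45) = 0.0660; 0.10/0.0660 − 1.645 = −0.13; power 44.9%.

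The stated 70% is met at about 95% success. The success rate behind the 90 patients is unstated whichever visit is chosen, so that is a separate question.

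**Is a single reading valid?** Claim non-inferiority if the Agresti-Caffo upper limit for Restorelle minus Vertessa is below 0.10. That limit is d + 1.645·√(a(1−a)/47 + b(1−b)/47), where a and b are (successes + 1)/47 in each arm and d = a − b. With a true 10-point deficit, the exact false-claim rate is 5.1% at 89% versus 79% and 5.6% at 95% versus 85%. Any one visit or window at these rates therefore gives a test near the nominal 5%.

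**How often do the two natural readings differ?** Failures are treated as permanent: successes at 12 months are binomial(45, p12), and successes through 24 months are binomial with that count as the number of trials and probability p24/p12. Results from 1,000,000 simulated trials per setting, equal arms:

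| Success at 12 → through 24 months | Claim at 12 | Claim through 24 | Readings differ |
|---|---|---|---|
| 89% → 88% | 43.7% | 41.5% | 8.4% |
| 95% → 94% | 67.0% | 61.4% | 11.2% |
| 89% → 85% | 43.6% | 36.9% | 18.5% |
| 95% → 92% | 67.1% | 52.4% | 23.0% |
| 95% → 89% | 67.1% | 43.6% | 32.4% |

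The spread follows second-year failures: one point gives about 8 to 11%, six points about 32%. The meshes are equal here, so neither reading can produce a false claim. Part of the disagreement reflects modest power.

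**What if the better of the two were chosen afterwards?** Same model, with Vertessa 10 points worse at both times:

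| Restorelle success at 12 → through 24 months | 12 months alone | Better of the two |
|---|---|---|
| 89% → 88% | 5.0% | 6.0% |
| 95% → 94% | 5.5% | 6.6% |
| 89% → 85% | 5.0% | 7.0% |
| 95% → 92% | 5.6% | 7.6% |
| 95% → 89% | 5.6% | 8.3% |

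The excess is about 1 to 3 percentage points. Rates of about 9 to 15% arise only if a pass at any of three separate visits counts as success, and the plan states no such procedure.

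**Carry-forward.** If every failure went untreated (the high-end case), status at 24 months and failure at any visit would differ on the claim in about 16 to 34% of equal-mesh trials. This assumes 89% or 95% success per visit and latent between-visit correlations from 0.97 down to 0.5. Retreated failures narrow the gap wherever retreatment is counted from surgery onward, which is the usual reading of that component.

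**The case for a change.** The strongest case for a change is that the endpoint cannot be coded from the protocol alone. No sentence makes the final visit the default, and 12 months is just as natural. Two defensible readings can split in up to about a third of trials, and a few sentences would remove the doubt with no new visits. The gap does not come from redaction, since the outcome and analysis text is intact.

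Most of that stands as a description. The time point and the carry-forward rule are absent, and a fuller statistical analysis plan would have named them. What does not stand is the step to an error. The plan describes one comparison, so the any-visit inflation belongs to a procedure nobody has proposed. The higher disagreement figures depend on assumed second-year failure rates that the documents do not supply. Any remedy would hand back blanks, namely which month and whether failures carry forward, on which competent statisticians could reasonably differ.

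The chart-review row of the task table, "Review of d/c summary, chart, postop Hct, complications (ER visits, etc", is marked at 6 months only in the readable table. This adds little, because Data Collection & Management lists record review under all three visits and the medical history update is marked at each, so retreatment can be captured throughout.

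**Conclusion.** The gap is genuine, but an analyst can fill it sensibly from data the plan already collects, so no change is called for. No stated rule produces a wrong result, and a single reading at 12 months or through 24 months keeps the false-claim rate at about 5 to 6%. The two readings would differ in about 8 to 32% of equal-mesh trials. Choosing the better of them after the fact would raise the false-claim rate to about 6 to 8%. These sizes assume 45 evaluable patients per arm, a 10-point absolute margin, permanent failures, and success rates of 85 to 95% that the documents do not give for the composite. The conclusion depends on one reading being settled before outcomes are compared by arm; it would not hold if non-inferiority were claimed on whichever visit happened to pass.

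### Does the absence of a named pessary item, and a record review ticked only at 6 months, leave the retreatment part of the primary outcome uncaptured?

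*Combined protocol and SAP*

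**What the plan says.** The Primary Outcome section lists four components, and the fourth is "retreatment for prolapse by either surgery or pessary". Three other places bear on how it would be recorded.

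- **Data Collection & Management, postoperative data.** The block opens "Postoperative data will include the following: 6, 12, 24 months". One of its bullets is "Review of electronic medical record (inpatient notes, d/c summary, ER visits), assessing for postoperative complications", and among the sub-items of that bullet is "Reoperation for recurrent POP". No sub-item mentions a pessary. In the extracted text the word occurs only in the Primary Outcome section. A figure that was not reproduced follows the list.
- **Office Interventions.** Women are seen at 6, 12 and 24 months, with a vaginal examination and a full POP-Q at each visit. The section adds: "Patients will also be asked to update their medical history".
- **Summary of tasks table.** The row beginning "Review of d/c summary, chart, postop Hct, complications (ER visits, etc" has one mark, at 6 months. The row "Update medical history" is marked at 6, 12 and 24 months, as is POP-Q.

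On form content, the REDCap paragraph says: "Data collection is customized for each study as based on a study-specific data dictionary defined by the research team". That dictionary is not part of the public document.

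**The concern.** Surgical retreatment has a named item and pessary retreatment has none, so half of a primary component seems to have nowhere to be written down. The record review is described by inpatient and emergency sources and aimed at complications, whereas pessary care would be expected in outpatient notes. Read literally, the task table also drops that review after 6 months, and the review is where the reoperation item sits.

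The component exists for a particular patient: a woman whose anatomy and symptoms look good because she has been retreated. If the retreatment is not recorded, she is scored a success. Failures missed at a similar rate in both arms shrink any true difference, and in a non-inferiority trial that favours the claim under test. The trial is small: with 45 evaluable women per arm, one misclassified woman moves an arm by 1/45 = 2.2 points against a 10-point margin.

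**Working it through.** **1. What the list is for.** The sub-items, including the reoperation item, hang from a record-review bullet whose stated aim is postoperative complications. Bothersome bulge, the third primary component, is not itemised there either. Pessary use is not a complication, so its absence from this list says little about whether it will be recorded.

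**2. Routes by which a retreatment would come to light.**

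| Route | 6 mo | 12 mo | 24 mo | Source |
|---|---|---|---|---|
| History update | yes | yes | yes | Office Interventions; task table |
| Vaginal examination | yes | yes | yes | Office Interventions |
| POP-Q | yes | yes | yes | Office Interventions; task table |
| Record review, per data list | yes | yes | yes | Data Collection & Management |
| Record review, per task table | yes | – | – | Summary of tasks |

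Only the last two rows disagree. The table row bundles the discharge summary, postoperative haematocrit and complications, which are largely perioperative. Several definitions in the data list are likewise limited to 14 or 30 days. A single perioperative review followed by history updates is a plausible reading. Under either reading, three routes remain at every postoperative visit.

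**3. Who could still be missed.** The woman must fail through component 4 alone, fail to report the retreatment, show no sign of it on examination and have no chart entry that anyone reads. A pessary in place would ordinarily be evident at a vaginal examination. If it is taken out for the POP-Q, any descent can be scored under components 1 and 2.

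**4. Illustrated size.** The documents give no retreatment rate and no success rate for the composite, so there is no figure of the plan's to reproduce on this point. Assumptions:

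- n = 90/2 = 45 per arm, from the Analysis Plan.
- True success is 89% versus 79%, exactly at the 10-point margin. The 89% is borrowed from the anatomic rate in the Background.
- q is the share of all failures hidden in this way, equal in both arms. It equals (share that are component-4-only) × (share of those missed).

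Expected true failures are 45 × 0.11 + 45 × 0.21 = 4.95 + 9.45 = 14.4. Hidden failures are 14.4 × q. Observed success is 1 − (1 − p)(1 − q), so the expected difference is 10 × (1 − q) points. Non-inferiority is declared when d + 1.645 × √[pR(1 − pR)/45 + pV(1 − pV)/45] < 0.10, where d = pR − pV is the observed difference. The probabilities come from exact binomial enumeration.

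| q | Example | Hidden failures, both arms | Expected difference | False non-inferiority, 89% vs 79% | Same, 94% vs 84% |
|---|---|---|---|---|---|
| 0 | – | 0 | 10.0 | 6.2% | 6.8% |
| 2% | 10% × 20% | 0.3 | 9.8 | 6.6% | 7.2% |
| 5% | 20% × 25% | 0.7 | 9.5 | 7.2% | 7.9% |
| 10% | 20% × 50% | 1.4 | 9.0 | 8.2% | 9.2% |

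The hidden-failure column is for 89% versus 79%. The 94% in the last column is borrowed from the subjective cure rate in the Background. The starting values above 5% come from the Wald rule at this sample size, not from missed retreatments. A normal approximation calibrated to start at 5% gives 5.7% at q = 5% and 6.6% at q = 10%, so the direction is the same and the size similar.

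The last row assumes that half of all component-4-only failures escape every route in step 2, which is hard to reconcile with three checks per visit. The 2% row is closer to what the plan would produce. It costs 6.6 − 6.2 = 0.4 points.

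**The case for a change.** The strongest case for acting is that the facts are right and the remedy is cheap. The extracted text names no pessary item, the table and the list do differ at 12 and 24 months, and a dated question about retreatment is a better instrument than an open invitation to update the history. The error also runs in the unsafe direction for a non-inferiority claim, and each arm is small enough for single patients to count.

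The textual points and the direction of the bias stand. What does not follow is that the plan loses these events. Anyone scoring the composite must determine component 4 for each woman, because the Primary Outcome section requires it, and the history and examination to do so are scheduled. Uneven misses between arms would matter more, but nothing in the design makes them likely: patients are blinded and the POP-Q examiner does not know the mesh. Whether a pessary field already exists cannot be judged from the public text, since both the dictionary and the figure after the list are unavailable. A short protocol that defers its fields to a dictionary need not list each one.

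**Conclusion.** No change to the plan is needed. The missing pessary item is form-level detail, and the single mark in the task table is a looseness between a summary and a fuller list. Both can be settled when the forms are built, without touching the outcome definition, the visits or the analysis. Followed as written, the plan should find nearly all retreatments.

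Under the stated assumptions the effect on a false non-inferiority claim is 0.4 points at q = 2%, and 2.0 points (8.2 − 6.2) even at the implausible 10%. Those figures rest on assumed success rates, equal misses in both arms and values of q that the documents do not supply. They illustrate scale and do not estimate it. No effect on the trial's conclusion can be shown from the documents. The schedule difference bears on the primary result only if that result is taken after 6 months, and the documents do not fix the primary time point; that is a separate matter.
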